### 7.4 Definition of Dose-Limiting Toxicity (DLT)

Any of the following events that occur during cycle 1 (first 4 weeks) will be considered a DLT when classified as possibly, probably or definitively related to investigational study treatment (according to NCI CTEP Adverse Event Reporting Requirements). Apart from the criteria listed below, if a lower grade AE leads to a dose interruption of more than 21 consecutive days of erdafitinib for the first 4 weeks of Cycle 1, this AE will be considered a DLT; patients must receive at least 75% of study drug during cycle 1 in order to be evaluable for the DLT observation period. Whenever a patient experiences toxicity that fulfills the criteria for a DLT, treatment with the study drug responsible for the toxicity will be interrupted (patient may continue the remainder study drugs) and the toxicity will be followed up. The Protocol Chair must be notified immediately of any DLT:

TOXICITY	DLT CRITERIA
Blood and lymphatic system disorders	Anemia CTCAE Grade $\geq$ 3 will not be considered DLT unless judged to be a hemolytic process secondary to erdafitinib.
	Febrile neutropenia CTCAE Grade $\geq$ 3
	ANC CTCAE Grade 3 for > 14 consecutive days
	ANC CTCAE Grade 4
	Platelet count CTCAE Grade 3 for > 7 consecutive days and/or with signs of bleeding
	Platelet count CTCAE Grade 4
Ocular disorders	CTCAE Grade $\geq$ 2 for > 21 days CTCAE Grade $\geq$ 3
General disorders and administration site conditions	Fatigue CTCAE Grade 3 for > 7 consecutive days
Skin and subcutaneous tissue disorders	Skin, mucosal or nail toxicity CTCAE Grade $\geq$ 3 for > 72 hours
Hyperphosphatemia	Phosphorus level $\geq$ 7.0 mg/dL for > 14 days despite treatment
GI disorders a	Diarrhea CTCAE Grade $\geq$ 3 for $\geq$ 48 hrs, despite the use of anti-diarrhea therapy
	Nausea/vomiting CTCAE Grade $\geq$ 3 for $\geq$ 48 hrs, despite the use of anti-emetic therapy
	Constipation CTCAE Grade $\geq$ 3 for $\geq$ 48 hrs, despite the use of anti-constipation therapy
Investigations b	Blood bilirubin c CTCAE Grade 2 for > 7 consecutive days or $\geq$ Grade 3
	AST or ALT CTCAE $\geq$ Grade 3
	Alkaline phosphatase CTCAE $\geq$ Grade 3
Other hematologic and non-hematologic toxicities	Any other CTCAE $\geq$ Grade 3 toxicity for > 7 consecutive days (except decreased lymphocyte count [lymphopenia] that is not clinically significant)

TOXICITY	DLT CRITERIA

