	
a Patients will not initially receive prophylactic treatment for nausea/vomiting during Cycle 1. However, prophylactic treatment may be initiated in all patients at the dose level where these toxicities have been observed and in all further patients if at least 1 patient has experienced nausea/vomiting CTCAE Grade <math>\geq</math> 3 or if at least 2 patients experienced nausea/vomiting CTCAE Grade <math>\geq</math> 2. However, anti-emetics may be applied for treatment if the patient has experienced nausea/vomiting CTCAE Grade <math>\geq</math> 1 at the discretion of the treating physician.
 
b For any hepatic toxicity CTCAE Grade 4, or CTCAE Grade 3 that does not resolve within 7 days to CTCAE Grade <math>\leq</math> 1 (or CTCAE Grade <math>\leq</math> 2 if liver infiltration with tumor present), an abdominal CT scan should be performed to assess if it is related to disease progression.
 
c Refers to total bilirubin.

	
Apart from the criteria listed above, if a lower grade AE leads to a dose interruption of more than 14 consecutive days of erdafitinib, this AE may be considered as DLT (the determination will be based on clinical significance and patient risk; discussion with the Protocol Chair will determine if the event should or should not count as a DLT).

Patients whose treatment is interrupted or permanently discontinued due to an AE or clinically significant laboratory value, must be followed as outlined in the table below, at least once a week for 4 weeks, and subsequently at 4-week intervals, until resolution or stabilization of the event, whichever comes first. Patients that require a dose delay of  $> 28$  days due to a cause unrelated to study participation will have the opportunity to continue study if deemed eligible to do so by the Protocol Chair of the study.

TOXICITY	FOLLOW-UP EVALUATION
Hematology	If $\geq$ CTCAE grade 3 neutropenia or $\geq$ CTCAE grade 3 thrombocytopenia have been demonstrated, these parameters must be repeated at least once a week until resolution to $\leq$ CTCAE grade 1 neutropenia or $\leq$ CTCAE grade 1 thrombocytopenia to allow for initiation of re-treatment.

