Renal	If creatinine $\geq 2 \times$ ULN has been demonstrated, this parameter must be evaluated at least twice a week until resolution to $\leq$ CTCAE grade 1 to allow for initiation of re-treatment, and then at least weekly until either resolution or until stabilization.  Creatinine $\geq 2.0 \times$ ULN and 3+ proteinuria or hematuria $\geq$ CTCAE grade 2 has been demonstrated, a 24-hour urine collection for total protein and total creatinine must be repeated at least weekly until either parameter returns to baseline value or until stabilization. Whenever a measured CrCl is obtained, a creatinine should be obtained within $\leq 72$ h of the urine collection.
Hepatic	If total bilirubin $\geq 2 \times$ ULN or $\geq$ CTCAE grade 3 AST/ALT has been demonstrated, these parameters must be repeated daily until resolution to $\leq$ CTCAE grade 1 (or $\leq$ grade 2 for AST or ALT, if liver metastasis are present) to allow for initiation of re-treatment, and then at least weekly until either resolution or until stabilization  Patients with total bilirubin $>$ ULN (any duration) should have fractionation of bilirubin into total/direct or indirect/direct components and any additional work-up as clinically indicated by

	these results. Follow-up of hyperbilirubinemia should proceed as per the guidelines above, irrespective of the results of fractionation.
Metabolic/Laboratory	Parameters of metabolic/ laboratory abnormalities $\geq$ CTCAE grade 3 must be assessed once at 2 to 4 days and once again at 7 days ( $\pm 1$ day) and be repeated twice a week until resolution to $\leq$ CTCAE grade 2 to allow for initiation of re-treatment, and then at least weekly until either resolution to $\leq$ CTCAE grade 1 or until stabilization.
	A CT scan or other imaging study to assess the pancreas, liver, and gallbladder must be performed within 1 week of the first occurrence of any $\geq$ CTCAE grade 3 of amylase or lipase levels.
	In patients with triglycerides $\geq 500$ mg/dL, urine amylase needs to be tested in addition.
Ocular toxicity	Patients who experience ocular toxicity should be followed as per Dose Modification guidelines (Section 8)
Non-Laboratory	Patients who experience non-laboratory DLTs must be evaluated at least once a week following demonstration of the toxicity until resolution of the toxicity to allow for re-treatment, stabilization of the toxicity, or study treatment completion.

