### 8.3.2 Dose Modification/ Delays and Toxicity Management

In the event of significant treatment-related toxicity, palbociclib and erdafitinib dosing may be interrupted or delayed and/or reduced as described below. In the event of multiple toxicities, dose modification should be based on the worst toxicity observed. Patients are to be instructed to notify investigators at the first occurrence of any adverse sign or symptom. Patients should not hold or discontinue palbociclib and erdafitinib for side effects potentially or likely related to concomitant anti-hormonal therapy (e.g., grade 3 or long lasting grade 2 joint pain) as per the investigator's judgment.

Missed doses are not made up. When the adverse event resolves, the cycle will continue as scheduled. However, if palbociclib or erdafitinib start for a specific cycle is delayed for toxicity, fulvestrant will continue without change.

The need for a dose reduction at the time of treatment resumption should be based on the table criteria below unless expressly agreed otherwise following discussion between the investigator and the Protocol Chair. If a dose reduction is applied, the patient may need to return to the clinic to receive new drug supply.

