Grade 2	
 
Omit dose of palbociclib and erdafitinib, and check AST and ALT daily until resolved to CTCAE Grade <math>\leq</math> 1, then                     
 
- If resolved in <math>\leq</math> 7 days, then maintain dose level of palbociclib and erdafitinib
 
- If resolved in <math>></math> 7 days, then <math>\downarrow</math> 1 dose level of palbociclib and erdafitinib. Start palbociclib first, and recheck AST and ALT levels in 7 days. If levels remain CTCAE Grade <math>\leq</math> 1, then reintroduce erdafitinib.
 
 
 

Grade 3	
 
Omit dose of palbociclib and erdafitinib, and check AST and ALT daily until resolved to CTCAE Grade <math>\leq</math> 1 (or CTCAE Grade <math>\leq</math> 2 in case of liver metastasis), then                     
 
- If resolved in <math>\leq</math> 7 days, then <math>\downarrow</math> 1 dose level of palbociclib and erdafitinib. Start palbociclib first, and recheck AST and ALT levels in 7 days. If levels remain CTCAE Grade <math>\leq</math> 1, then reintroduce erdafitinib.
 
- If resolved in <math>></math> 7 days, then discontinue patient from palbociclib and erdafitinib
 
 
 

Grade 4	Discontinue palbociclib and erdafitinib.

AST or ALT and Bilirubin	
AST or ALT > 3.0 – 5.0 ULN and total bilirubin > 2.0 x ULN	Omit dose of palbociclib and erdafitinib, , and check bilirubin, AST and ALT daily until resolved to CTCAE Grade ≤ 1, then 
 
- If resolved in ≤ 7 days, then ↓ 1 dose level of palbociclib and erdafitinib. Start palbociclib first, and recheck bilirubin, AST and ALT levels in 7 days. If levels remain CTCAE Grade ≤ 1, then reintroduce erdafitinib.
 
- If resolved in > 7 days, then discontinue patient from palbociclib and erdafitinib.
 

AST or ALT > 5.0 ULN and total bilirubin > 2.0 x ULN	Discontinue palbociclib and erdafitinib.
Metabolism and nutrition disorders (for erdafitinib only)	
Phosphorus elevationa	
5.5-6.9 mg/dL	Maintain dose level of erdafitinib. May consider sevelamer 800 mg to 1,600 mg 3 times a day (with food).

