Grade 3	Hold erdafitinib (for up to 28 days), with weekly reassessments of clinical condition.  Silver nitrate application weekly AND topical antibiotics (Mupirocin 2%, gentamycin, bacitracin zinc/polymixin B) AND vinegar soaks (soaking fingers or toes in a solution of white vinegar in water 1:1 for 15 minutes every day).  For signs of infection (periungal edema/erythema/ tenderness and/or discharge), start the following: treatment with oral antibiotic for 2 weeks (cefadroxil 500 mg BID, ciprofloxacin 500 mg BID, or sulfamethoxazole/trimethoprim (Bactrim®) DS BID).  For cases of severe/refractory infection consider intravenous antibiotics.  Consider dermatological and/or surgical evaluation if necessary.  When resolved to ≤Grade 1 or baseline, restart at 1 dose level below in consultation with the medical monitor.

Grade 4	Discontinue erdafitinib, evaluation and therapy as clinically indicated.
General disorders (for erdafitinib only)	
Fatigue/ asthenia	
Grade 1 / 2	Maintain dose level of erdafitinib.
Grade 3	Omit dose of erdafitinib until resolved to CTCAE Grade $\leq 1$ , then - If resolved in $\leq 7$ days, maintain dose level of Erdafitinib. - If resolved in $> 7$ days, discontinue patient from Erdafitinib.
Other AEs	
Grade 1 / 2	Maintain dose level of palbociclib and erdafitinib.
Grade 3	Omit dose of palbociclib and erdafitinib until resolved to CTCAE Grade $\leq 1$ , then $\downarrow$ dose level of palbociclib and erdafitinib.
Grade 4	Discontinue palbociclib and erdafitinib.

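### For a Grade 3 laboratory value with no row of its own in Section 8.4, Section 7.4 allows re-treatment at Grade 2 while Section 8.4 holds both oral drugs until Grade 1

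*Combined protocol and SAP*

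**What the plan says.** Section 7.4 follows the DLT criteria with a follow-up table. It covers patients whose treatment is interrupted or stopped for an AE or a clinically significant laboratory value, whether or not the event is a DLT; they "must be followed as outlined in the table below". The Metabolic/Laboratory row applies to abnormalities of Grade 3 or higher. It has them rechecked until they are at or below "CTCAE grade 2 to allow for initiation of re-treatment", and after that at least weekly until Grade 1 or stabilization.

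Section 8.4 has laboratory rows for neutrophils, anemia, febrile neutropenia, platelets, total bilirubin, AST/ALT, AST/ALT combined with bilirubin, and phosphorus. Anything else falls to 'Other AEs', where the Grade 3 instruction is "Omit dose of palbociclib and erdafitinib until resolved to CTCAE Grade" 1 or lower, followed by a dose reduction of both drugs. Section 13.2.1 counts laboratory abnormalities as adverse events, so 'Other AEs' reaches them.

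Section 8.3.2 introduces these tables. It sends interruptions, delays and reductions to them and adds: "The need for a dose reduction at the time of treatment resumption should be based on the table criteria below", unless the investigator and the Protocol Chair agree otherwise.

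**The concern.** Two current instructions give different restart grades for the same event. A patient whose Grade 3 value has fallen to Grade 2 may be re-treated under 7.4 and must still be held under 8.4. The trial runs at five centers (the coordinating center plus four consortium sites), so the same value could be handled in two ways. The looser reading restarts an investigational FGFR inhibitor together with palbociclib while the abnormality is still Grade 2.

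The length of a hold also enters two other rules: discontinuation after a delay of more than 28 days (8.4) and the requirement to receive at least 75% of study drug in cycle 1 to be evaluable for DLT (7.4).

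**Working it through.** The plan states no figure on this point, so the check is a comparison of texts.

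**1. Are the 7.4 levels really restart levels?** For Grade 3 events:

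| Event | Restart level in 7.4 | Restart level in 8.4 | Match |
|---|---|---|---|
| AST/ALT | Grade 1, or Grade 2 with liver metastasis | Grade 1, or Grade 2 with liver metastasis | Yes |
| Platelets | Grade 1 | Grade 1 | Yes |
| Neutrophils | Grade 1 | ANC 1000/mm3 or above (palbociclib) | No, 7.4 stricter |
| Ocular | Refers to Section 8 | Own rules | Yes, by reference |
| Laboratory value with no 8.4 row | Grade 2 | Grade 1 | No, 7.4 looser |

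The AST/ALT line is telling. The 7.4 exception, "grade 2 for AST or ALT, if liver metastasis are present", reappears in 8.4 as "in case of liver metastasis". The 7.4 table therefore carries dosing thresholds as well as a recheck schedule. In the Metabolic/Laboratory row, Grade 1 appears only as the later monitoring endpoint, so Grade 2 is the restart level.

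The protocol does not print the CTCAE cut-points for neutrophils. I take 1000/mm3 as the lower edge of Grade 2, because 8.4 doses Grades 1 and 2 without a hold and releases a Grade 3 hold at 1000/mm3.

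**2. Which values are affected?** The study calendar schedules 14 chemistry analytes plus magnesium and phosphorus: 14 + 2 = 16.
- Own row in 8.4: total bilirubin, AST, ALT, phosphorus (4).
- Set aside: creatinine, because the 7.4 Renal row uses Grade 1 and agrees with 'Other AEs'; and calcium, because Grade 3 hypocalcemia sits in the 8.4 phosphorus row (2).
- Remainder: 16 - 4 - 2 = 10. These are sodium, potassium, chloride, bicarbonate, BUN, glucose, total protein, albumin, magnesium and alkaline phosphatase.

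The documents do not show which of the 10 carry CTCAE grades, so 10 is an upper count for the scheduled panel. Amylase and lipase are outside that panel, but the Metabolic/Laboratory row itself mentions them and 8.4 has no row for them.

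**3. What could a longer hold do to the 75% rule?** This is illustration only; none of the timings comes from the documents. Assume a Grade 3 value on Day 8 of cycle 1, 3 days to reach Grade 2, and D further days to reach Grade 1. Planned doses are 28 for erdafitinib and 21 for palbociclib, 49 together.

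| Rule | Erdafitinib | Palbociclib | Both pooled |
|---|---|---|---|
| 7.4 (restart at Grade 2) | 25/28 = 89.3% | 18/21 = 85.7% | 43/49 = 87.8% |
| 8.4, D = 3 | 22/28 = 78.6% | 15/21 = 71.4% | 37/49 = 75.5% |
| 8.4, D = 5 | 20/28 = 71.4% | 13/21 = 61.9% | 33/49 = 67.3% |
| 8.4, D = 14 | 11/28 = 39.3% | 7/21 = 33.3% | 18/49 = 36.7% |

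At D = 14 palbociclib misses Days 8 to 21 only, because Days 22 to 28 are off drug. At D = 3 the patient fails the 75% rule if it is applied to each drug and passes if the two oral drugs are pooled. The plan does not say which is meant.

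**The case against.** The strongest reply is that 8.4 already controls. Section 8.3.2 points interruptions and reductions to its tables, 8.5 requires advance discussion of departures, and the 7.4 table is headed as follow-up. A site that waits for Grade 1 satisfies both texts. Much of this stands: a careful site would probably follow 8.4. But the 8.3.2 sentence on resumption concerns dose reduction, not the restart grade, and nothing says that 8.4 prevails over the level written in 7.4. Where Section 8 was meant to govern, the Ocular row says so; the Metabolic/Laboratory row does not.

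A second reply concerns alkaline phosphatase. It is a named DLT ("Alkaline phosphatase CTCAE" Grade 3 or higher) and is listed with bilirubin and AST/ALT. A footnote there addresses hepatic toxicity generally, with resolution to Grade 1, or Grade 2 with liver infiltration. A site could treat it as hepatic and use Grade 1, in line with 8.4. That is reasonable, although the 7.4 Hepatic row names only bilirubin and AST/ALT. Alkaline phosphatase is thus an arguable example, while electrolytes, glucose, amylase and lipase are not open to that reading. In cycle 1 a DLT also goes to the Protocol Chair at once, and cross-site calls run every other week during escalation, so unnoticed divergence is less likely there.

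A reader might infer that the mismatch changes DLT counts or decides who is evaluable. The documents do not support that. A Grade 3 alkaline phosphatase that qualifies as a DLT counts whichever restart text is used. For other values the result depends on assumed recovery times and on how the 75% rule is read. Two more provisions intervene. An erdafitinib interruption of more than 14 consecutive days for a lower-grade event may be judged a DLT (in the illustration, from D = 12, a 15-day hold). Section 7.11 ties replacement to discontinuation clearly unrelated to treatment.

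A reader might also see a contradiction in 7.4 naming no dose reduction. That is silence; 7.5 and 8.4 require one.

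**Conclusion.** The mismatch holds as a drafting conflict with a safety side. For a Grade 3 laboratory value without its own 8.4 row, the plan contains a written permission to re-dose at Grade 2 that 8.4 forbids. The gap is one CTCAE grade and concerns Grade 3 events; at Grade 4, 8.4 discontinues both drugs. What is at stake is safe and consistent re-dosing across sites. No stated statistical quantity changes. Any effect on the 75% rule or the 28-day limit is illustrative, because the documents give neither event rates nor recovery times. The conclusion rests on reading 'Other AEs' as covering laboratory abnormalities, which 13.2.1 supports, and on the absence of any text ranking 7.4 against 8.4 on the restart grade. The Hematology row has a mismatch of the same kind in the opposite direction.

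**What to change.** In the 7.4 Metabolic/Laboratory row, replace the Grade 2 re-treatment level with: *until the restart level in Section 8.4 is met*. Keep the recheck schedule and the later monitoring to Grade 1 or stabilization. Make the same deferral in the Hematology row, so that neutropenia has one restart level.

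A separate alkaline phosphatase row in 8.4 is not needed. It would mostly repeat 'Other AEs', and it would fix omission of both drugs where 7.4 interrupts, for a DLT, only the drug held responsible. The DLT table stays unchanged.

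The cost is two wording edits, with no new test, visit or drug supply. For the Metabolic/Laboratory row the stricter existing rule is kept, so some holds become slightly longer at sites that would have followed 7.4. A patient who enters with a raised value, such as Grade 2 alkaline phosphatase (4.1.10 sets no limit), may be slow to reach Grade 1. That is already so under 8.4, and 8.3.2 and 8.5 leave room for agreement with the Protocol Chair. For neutropenia the deferral works the other way: palbociclib could restart at an ANC of 1000/mm3 without waiting for Grade 1. If the sponsor intends the stricter level, 8.4 should be changed to say so. Platelets are unaffected.

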## 7.5 Definition of Maximum Tolerated Dose (MTD)

The MTD will be defined as the highest dose at which 20% of the patients experienced a DLT. The first cohort of patients (3 patients) will be started at dose level 1, and each patient will be observed for 4 weeks on the specified dose. No new cohort of patients will be treated until the previous cohort has been fully evaluated for toxicity and a dose escalation decision has been made. Routine updates regarding patient and study status will be conducted.

Once the MTD is reached, the safety data will be analyzed and the expansion component of the study will be completed to assess tolerability and efficacy. Patients in the phase II portion of the study will initiate study treatment at the MTD defined in the escalation component of the trial. Note that dose reduction within patients (individually) is allowed after the 4 week DLT observation period in the escalation and in the expansion components of the study (see Dose Modification guidelines, Section 8). Intrapatient dose escalation will not be allowed. Dose reduction will be required for a given patient in case of:

- Grade 3 or 4 toxicities
- Grade  $\geq 2$  hyperphosphatemia lasting more than 21 days despite medical treatment, or
- Grade  $\geq 2$  ocular toxicity lasting more than 28 days despite medical treatment, or
- Grade  $\geq 2$  elevation of creatinine, bilirubin, AST, or ALT lasting more than 14 days despite medical treatment, or
- Grade  $\geq 2$  skin or nail toxicity for more than 28 days in a row despite optimal medical treatment, or

- Grade  $\geq$  2 GI toxicity lasting more than 14 days despite medical treatment.

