7.0-9.0 mg/dL	Omit erdafitinib.  Sevelamer 800 to 1,600 mg 3 times a day with food until phosphate level is <5.5 mg/dL.  Once serum phosphate level returns to <5.5 mg/dL, restart erdafitinib at same dose level.  A dose reduction may be implemented for persistent hyperphosphatemia (≥7 mg/dL) if clinically necessary
>9.0 mg/dL	Omit erdafitinib.  Sevelamer up to 1,600 mg 3 times a day with food  AND  Acetazolamide 250 mg 2 or 3 times a day only until serum phosphate level returns to <5.5 mg/dL.  Once serum phosphate level returns to <5.5 mg/dL, restart treatment at the first reduced dose level.  A second dose reduction may be implemented if needed or clinically indicated for persistent hyperphosphatemia (≥7 mg/dL) at every cycle
>10.0 mg/dL and/or significant alteration in baseline renal function and/or Grade 3 hypocalcemia	Erdafitinib should be discontinued permanently. (In situations where the subject is having clinical benefit and the investigator and the Study Chair agree that re-starting drug is in the best interest of the subject, the drug may be re-introduced at 2 dose levels lower if appropriate. Follow other recommendations described above.)
aNote: Restriction of phosphate intake to 600 – 800 mg/day is recommended to all subjects in the study	
Ocular toxicity (for erdafitinib only)	
Grade 1	Refer to ophthalmologic exam. If this cannot be performed within 7 days, omit erdafitinib until an exam can be performed.  If no evidence of eye toxicity, continue erdafitinib at same dose level.

	
If keratitis or retinal abnormality are detected, omit erdafitinib until signs and symptoms have resolved; follow specific treatment as per ophthalmologist's recommendations.
 
For retinal pathology perform OTC as appropriate and consider referral to a retina specialist for further evaluation.
 
If toxicity is reversible (complete resolution or stabilization and asymptomatic) in 4 weeks according to ophthalmologic exam, resume erdafitinib at the next lower dose level after consultation with Protocol Chair.
 
Monitor for recurrence every 1 to 2 weeks for a month and as clinically appropriate thereafter. If there is no recurrence then re-escalation can be considered in consultation with the medical monitor.
 
If there is no evidence of eye toxicity, continue erdafitinib therapy at the same dose level.

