## 8.5 Special Considerations

- If erdafitinib needs permanent discontinuation, patients may continue fulvestrant and palbociclib treatment under study procedures
- If palbociclib needs permanent discontinuation, patients may continue fulvestrant and erdafitinib treatment under study procedures
- If both erdafitinib and palbociclib need permanent discontinuation, patients should discontinue all study drugs
- For toxicities considered (by the treating investigator) unlikely to develop into serious or life-threatening events (e.g. alopecia, dysgeusia), treatment may be continued at the same dose without reduction or interruption
- The treating investigator may reduce a subject's dose for a toxicity of any grade/duration where s/he believes it to be in the best interest of the subject
- Any consideration to alter the above dose modification guidelines should be discussed with the Protocol Chair for approval or disapproval in advance

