**Table 17.2.1**

		Number of Patients																	
		1	2	3	4	5	6	7	8	9	10	11	12	13	14	15	16	17	18
Number of Patients with DLTs	0	E	E	E	E	E	E	E	E	E	E	E	E	E	E	E	E	E	
	1	D	D	S	S	S	S	S	E	E	E	E	E	E	E	E	E	E	
	2	D	DU	D	S	S	S	S	S	S	S	S	S	S	S	S	E	E	
	3	DU	DU	DU	DU	D	S	S	S	S	S	S	S	S	S	S	S	S	
	4	DU	DU	DU	DU	DU	DU	D	S	S	S	S	S	S	S	S	S	S	
	5	DU	DU	DU	DU	DU	DU	DU	DU	DU	S	S	S	S	S	S	S	S	
	6	DU	DU	DU	DU	DU	DU	DU	DU	DU	DU	DU	DU	DU	DU	S	S	S	
	7	DU	DU	DU	DU	DU	DU	DU	DU	DU	DU	DU	DU	DU	DU	DU	DU	DU	
	8	DU	DU	DU	DU	DU	DU	DU	DU	DU	DU	DU	DU	DU	DU	DU	DU	DU	
	9	DU	DU	DU	DU	DU	DU	DU	DU	DU	DU	DU	DU	DU	DU	DU	DU	DU	
	10	DU	DU	DU	DU	DU	DU	DU	DU	DU	DU	DU	DU	DU	DU	DU	DU	DU	
	11	DU	DU	DU	DU	DU	DU	DU	DU	DU	DU	DU	DU	DU	DU	DU	DU	DU	
	12	DU	DU	DU	DU	DU	DU	DU	DU	DU	DU	DU	DU	DU	DU	DU	DU	DU	
	13	DU	DU	DU	DU	DU	DU	DU	DU	DU	DU	DU	DU	DU	DU	DU	DU	DU	
	14	DU	DU	DU	DU	DU	DU	DU	DU	DU	DU	DU	DU	DU	DU	DU	DU	DU	
	15	DU	DU	DU	DU	DU	DU	DU	DU	DU	DU	DU	DU	DU	DU	DU	DU	DU	

16												DU	DU	DU
17												DU	DU	
18														DU

**E:** Escalate to the next higher dose; **S:** Stay at the same dose; **D:** De-escalate to the previous lower dose; **DU:** De-escalate to the previous lower dose and the current dose will never be used again in the trial;

No new cohort of patients will be treated until the previous cohort has been fully evaluated for toxicity. All patients treated to determine the MTD will be part of the escalation portion of the trial.

Once the MTD is reached, the safety data will be analyzed and the expansion component of the study will be completed to assess tolerability and efficacy. Patients in the expansion component of the study will initiate study treatment at the respective MTD. Note that dose reduction within individual patients is allowed in the expansion component of the study. Dose reduction will be required for a given patient in case of grade 3 or 4 toxicities, or if grade 2 creatinine, bilirubin, AST, ALT, hyperphosphatemia or grade 2 GI toxicity lasting more than 2 weeks.

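### A patient whose erdafitinib is reduced for toxicity in cycle 1 can by default be counted as DLT-free at the assigned level: Sections 7.5, 8.4 and 8.5 conflict on timing, and Sections 7.4 and 17.2.1 do not say how to score it

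*Combined protocol and SAP*

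**What the plan says.** Sections 7.5 and 17.2.1 both set the observation condition: "each patient will be observed for 4 weeks on the specified dose". Section 7.5 then places individual reduction after that window, for escalation and expansion alike: "Note that dose reduction within patients (individually) is allowed after the 4 week DLT observation period". Section 17.2.1, below Table 17.2.1, mentions it for one component: "Note that dose reduction within individual patients is allowed in the expansion component of the study".

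The dose-modification table in Section 8.4 has no cycle-1 exception. For phosphorus above 9.0 mg/dL it says: "Once serum phosphate level returns to <5.5 mg/dL, restart treatment at the first reduced dose level". Section 8.5 adds: "The treating investigator may reduce a subject's dose for a toxicity of any grade/duration where s/he believes it to be in the best interest". Section 8.3.2 lets the investigator and the Protocol Chair agree to depart from the table.

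Section 7.4 defines DLTs by graded events, most with a minimum duration, and by long interruptions of erdafitinib (more than 21 consecutive days is a DLT; more than 14 may be). For phosphorus the DLT threshold is a level of at least "7.0 mg/dL for > 14 days despite treatment". On exposure it says: "patients must receive at least 75% of study drug during cycle 1 in order to be evaluable for the DLT observation period". It does not mention dose reduction.

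**The concern.** DLT in cycle 1 and the MTD are the primary endpoints. The mTPI table takes as input a count of DLTs among patients treated at a level. That count means what it should only if a patient entered as DLT-free was in fact followed on that dose.

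When Sections 8.4 and 7.4 are followed as written, a patient can be taken off the assigned dose for toxicity, miss every DLT criterion, pass the exposure rule and be left in the denominator as a non-event. Toxicity that led to a reduction is then read as tolerance. The error has one direction: it lowers the apparent DLT rate and so tends to raise the MTD. At least 20 expansion patients then start at that MTD.

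**Working it through.** **1. The plan's own decisions.** Section 17.2.1 gives a target of 0.20 with a margin of 0.05 each side, so the interval is 0.15 to 0.25. It states that 0/3 means escalate and 1/3 means stay. I assume a Beta(1,1) prior, which is not stated, and divide posterior mass by interval width:

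- 0/3, Beta(1,4): below 0.478/0.15 = 3.19; within 0.206/0.10 = 2.06; above 0.316/0.75 = 0.42. Escalate.
- 1/3, Beta(2,3): below 0.110/0.15 = 0.73; within 0.152/0.10 = 1.52; above 0.738/0.75 = 0.98. Stay.

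Both stated decisions are reproduced.

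**2. Reduction triggers that are not DLTs (Section 8.4 against Section 7.4).**

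- Phosphorus above 9.0 mg/dL: held, then restarted one level lower. A DLT only if at least 7.0 for more than 14 days.
- Grade 3 constipation: held, then one level lower. A DLT only if it lasts 48 hours or more despite therapy.
- Other Grade 3 events: held, then lowered. A DLT only if longer than 7 consecutive days.

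The phosphorus case is plausible in cycle 1. Section 8.1.3.2 reports that phosphate peaked between cycles 1 and 2, with the highest mean, 7.3 mg/dL, on Cycle 1 Day 21 at 9 mg. That dose is above this trial's top level, but the rises were dose dependent. The study calendar tests phosphorus on days 1, 8, 15 and 22. An elevation first found on day 15 has only days 15 to 28, which is 14 days, inside the window, so it cannot exceed 14 days there.

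**3. Does the 75% rule catch the reduction?** For a reduction from dose a to dose b after f full-dose days and k held days, the share of the planned cycle-1 dose is [f·a + (28 − f − k)·b] / (28·a).

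| Step | From day 2, no hold | Longest hold from day 15 that passes | One day longer |
|---|---|---|---|
| 8 to 6 mg | 170/224 = 75.9% | 4 days: 172/224 = 76.8% | 166/224 = 74.1% |
| 6 to 5 mg | 141/168 = 83.9% | 5 days: 129/168 = 76.8% | 124/168 = 73.8% |
| 5 to 4 mg | 113/140 = 80.7% | 5 days: 106/140 = 75.7% | 102/140 = 72.9% |

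The day-2 column is a bound. The Section 8.4 triggers above all start with a hold, so only Section 8.5 could produce that case. The later holds are the relevant ones. A patient held from day 22 to day 28 has 21/28 = 75.0%, passes, and can restart one level lower in cycle 2 without any reduction inside cycle 1. Seven held days in the window are also short of both interruption clauses.

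**4. How often.** The documents give no rate of non-DLT cycle-1 reductions, so I assume q per patient. P(at least one in a cohort of 3) = 1 − (1 − q)³:

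- q = 10%: 1 − 0.729 = 27%
- q = 20%: 1 − 0.512 = 49%
- q = 30%: 1 − 0.343 = 66%

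With a true DLT rate of 20%, P(0/3) = 0.8³ = 0.512. If a further 10%, 20% or 30% of patients are reduced without a DLT, the chance that all three are DLT-free and unreduced is 0.7³ = 0.343, 0.6³ = 0.216 or 0.5³ = 0.125. Then 33%, 58% or 76% of first-cohort escalations would include at least one reduced patient.

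**The case against.** The strongest reply is that a reader might infer that Section 7.4 positively scores a reduced patient as DLT-free, and it does not. It is silent. Sections 7.5 and 17.2.1 ask for four weeks on the specified dose, so one could equally say that a reduced patient is not evaluable. Section 7.5 also never writes the word only, and it refers the reader to Section 8. This stands as a correction of strength: the DLT-free count is a default, because a reduction is neither a DLT nor a stated reason for non-evaluability. Two readings of a primary-endpoint count are still open.

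Other limits also stand:

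- Section 8.4 can be varied with Protocol Chair agreement. Resumption at a lower dose after Grade 2 ocular toxicity also requires clinical benefit, so it is a weak cycle-1 example.
- Not every reduction is affected. Some triggers, such as Grade 3 AST or ALT, are DLTs themselves. Long early holds fall below 75%.
- A reader might infer that the trial could escalate from 8 mg on such patients. It cannot, because 8 mg is the top level. There the effect is on declaring the MTD.
- The recommended phase II dose needs at least 15 of 20 patients tolerating 8 weeks. That is a real safeguard, but it acts only after expansion patients have started at the MTD.

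A reader might also infer that every treatment-related reduction should be scored as a DLT. The documents do not settle this, and it has a price. With a 20% DLT rate and an independent 20% reduction rate, the scored rate becomes 1 − 0.8 × 0.8 = 36% against a 20% target. P(0/3) falls from 51% to 0.64³ = 26%, and P(at least 2/3) rises from 10% to 30%.

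**Conclusion.** The point holds as a conflict between sections combined with a missing counting rule on the primary endpoint. Sections 7.5 and 17.2.1 presuppose four weeks on the assigned dose. Sections 8.4 and 8.5 lead to reductions in that window for events that are not DLTs. Neither the interruption clauses nor the 75% rule reliably removes those patients from the DLT-free count. The tendency is towards an MTD that is too high.

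The size is uncertain. The 27% to 66% range rests wholly on the assumed 10% to 30% per patient. The exposure figures assume that the 75% is measured on erdafitinib dose. If days were counted instead, a reduced patient would pass more easily. The documents do not support saying that every reduced patient is miscounted, or that the plan expressly scores such patients as DLT-free.

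**What to change.** Reconcile Sections 7.4, 7.5, 8.4, 8.5 and 17.2.1 on whether an erdafitinib reduction may occur in cycle 1 during escalation. Which clinical rule applies is for the sponsor, and nothing here proposes one.

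Then add a counting rule to Sections 7.4 and 17.2.1: a patient whose erdafitinib is reduced during cycle 1, or is held in cycle 1 and restarted at a lower level, for a treatment-related adverse event is not counted as DLT-free at the assigned level. The second clause is needed for the patient held late in cycle 1 who restarts lower in cycle 2.

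The sponsor should prespecify one of two treatments:

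- **Adjudicate as a DLT.** This keeps the toxicity information but can move the scored rate away from the 20% target.
- **Not evaluable and replaced.** This avoids the false credit but discards the information. Since Table 17.2.1 also lists 0/2 as escalate, the text should say that the decision waits for the replacement patient.

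The cost is a few sentences, plus an occasional replacement patient or an extra cohort at a level.
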